4.6. Subject Withdrawal

At the time of early withdrawal, the subject should complete the Day 14/Early Withdrawal (EW) visit and return in 7 – 12 days for the End-of-Study Visit. A subject may withdraw from the clinical trial at any time without penalty and for any reason without prejudice to his or her future medical care. Subjects will be informed that the Investigator may withdraw any subject from the study without his/her consent for any reason if the Investigator thinks it is in the best interest of the subject. In such cases, the Investigator will contact the Sponsor's Medical Monitor before subject withdrawal.

4.6.1. Criteria for Withdrawal from Clinical Trial

Reasons for subject withdrawal include, but are not limited, to the following:

- Withdrawal of consent

- Adverse events
- Pregnancy
- Protocol violation/non-compliance
- Study burden
- Positive test for COVID-19
- Fear of contracting COVID-19
- Sponsor termination of the study
- Investigator's determination that it is in the best interest of the subject to discontinue
- Lost to follow-up
- Other (e.g., withdrawal of caregiver consent)

The reason for withdrawal must be recorded on the case report form (CRF). Whenever possible, the subject should continue to be followed for safety assessments (if consent has not been withdrawn). The Sponsor's Medical Monitor should be contacted before withdrawal whenever possible.

4.6.2. End-of-Study for Early Withdrawal Subjects

Subjects who discontinue the study after the Day -1 visit of either Treatment Period and who have received study drug will have Early Withdrawal and End-of-Study visits.

5. SCHEDULE OF EVENTS AND STUDY PROCEDURES

Assessments and procedures at each visit are summarized in the Schedule of Events. For visits in which multiple disease assessments are planned, efforts should be made to conduct them after the subjects have been provided with a light meal or snack (without caffeinated beverages or high sugar content) in the following order (as relevant): FERT before pVFT, then DSST and CANTAB. The Color Trails Test should be conducted after the CANTAB assessments. ADCS-CGIC should be conducted last. SAS-6, GDS-30 and CAARS may be administered at any time before ADCS-CGIC.

5.1. Visit Assessments

5.1.1. Screening (Day -28 to Day -2)

The following procedures will be performed, and assessments/measurements recorded:

- Consenting process and written informed consent
- Obtain a subject number from the IWRS
- Evaluation for inclusion/exclusion criteria

- Demographics (sex, age, race, ethnicity, years of education)
- Medical history including concomitant medications
- Height, body weight, BMI calculation
- Vital signs (blood pressure [BP], heart rate [HR], respiration rate and oral/tympanic temperature); for assessments of orthostatic changes, BP and HR are obtained: a) after rest in a supine position for at least 5 minutes, and b) 1 minute after standing
- 12-lead ECG, obtained 3 times (separated by approximately 1 minute) after the subject is supine for at least 5 minutes
- Complete physical examination, excluding genital, rectal and breast exams
- Laboratory tests
 1. Hematology, fasting chemistry (includes calculated creatinine clearance), and urinalysis
 2. Urine drug screen
 3. Alcohol breath test
 4. Serology for HIV, hepatitis B and C
 5. SARS-CoV-2 test
 6. Serum β-hCG test for females of childbearing potential
 7. FSH test for postmenopausal women
 8. Whole blood sample for determination of genetic variants including but not limited to APOE4, LRRK2, and GBA (optional and where applicable)
 9. Plasma sample for neurodegenerative biomarkers
- CANTAB administered twice, at least 1 hour apart during the final week (Day -8 to Day -2) before Treatment Period 1 to familiarize subjects with the tests.
- Other clinical and cognitive scales/assessments:
 1. MoCA
 2. ADCS-CGIC
 3. DSST
 4. RBD1Q (to be evaluated in all subjects, but to be used to assess eligibility for subjects with PD only)
 5. MHYS (only in subjects with PD; prior assessment within 3 months of Screening will suffice)
 6. C-SSRS

Subjects with a positive drug or alcohol screen at Screening will be rechecked once and if positive, the subject will be excluded from participation in the study. The drug and/or alcohol screen tests may be repeated per Investigator clinical judgement.

Subjects who are eligible for study participation will be scheduled to return to the clinic for the start of Treatment Period 1.

5.1.2. Day -1, one day before start of dosing of Study Drug in Treatment Periods 1 and 2

The following procedures will be performed, and assessments/measurements recorded:

- Review of inclusion/exclusion criteria (Treatment Period 1 only)
- Assessment of concomitant medications
- Vital signs (BP, HR, respiration rate, and oral/tympanic temperature); for assessments of orthostatic changes, BP and HR are obtained: a) after rest in a supine position for at least 5 minutes, and b) 1 minute after standing
- 3 sets of triplicate ECG measures (i.e., 9 ECGs) prior to dosing with study drug to thoroughly establish a baseline obtained after subject has rested in supine position for at least 5 minutes; the time between each set of 3 ECGs should be \leq 5 minutes
- Alcohol breath test prior to dosing CST-107 or matching placebo
- Serum or urine pregnancy test (per standard site practice) prior to dosing CST-107 or matching placebo for females of childbearing potential; positive urine pregnancy result to be confirmed by serum test

The following procedures will be administered (prior to dosing CST-107) at approximately the same time of day (\pm 1 hour) and under approximately the same food status as planned for the tests on Days 1, 7, and 14:

- FERT
- pVFT
- DSST
- CANTAB
- Color Trails Test (select sites only), administered after CANTAB
- SAS-6
- CAARS
- GDS-30
- C-SSRS in Treatment Period 2 only

Obtain the randomization number and the Days 1-7 blister card/bottle numbers for study drug (CST-2032+CST-107 or matching placebos) from the IWRS – do not dispense blister card/bottle to the subject

Remove one CST-107 or matching placebo tablet from the bottle or the Day 10 well on the blister card and administer the dose to the subject after completion of all scheduled assessments

5.1.3. Day 1, Treatment Periods 1 and 2

The following procedures will be performed, and assessments/measurements recorded:

- Assessment of concomitant medications
- Vital signs (BP, HR, respiration rate, and oral/tympanic temperature); for assessments of orthostatic changes, BP and HR are obtained: a) after rest in a supine position for at least 5 minutes, and b) 1 minute after standing:
 1. Within 30 minutes prior to dosing of study drug
 2. 4 hours (\pm 30 minutes) after dosing study drug
- 12-lead ECG, obtained 3 times (separated by approximately 1 minute) after subject has rested in supine position for at least 5 minutes:
 1. Within 30 minutes prior to dosing study drug
 2. Approximately 1 hour after dosing study drug
 3. Approximately 2 hours after dosing study drug
 4. Approximately 4 hours after dosing study drug
- Laboratory tests (hematology, chemistry, and urinalysis)
 1. Pre-dose and approximately 4 hours post-dose
 2. Chemistry only at 4 hours post-dose
- Administer study medication (CST-2032 and CST-107 or matching placebos) from the blister card/bottle
- FERT administered at least 2 hours after dosing study drug and prior to administration of the cognition tests (pVFT, DSST, CANTAB)
- SAS-6, CAARS GDS-30 administered at least 2 hours after dosing study drug
- pVFT, DSST, CANTAB tests at 3 hours (\pm 30 minutes) after dosing study drug. Tests should be conducted at approximately the same time of day (\pm 1 hour) and under the same food status on Days -1, 1, 7 and 14.
- Dispense study medication (Days 1-7 blister card/bottle) and provide dosing instructions to the subjects
- Dispense dosing diary
- Assessment of AEs
- Schedule Day 7 Visit. Subjects should be instructed not to administer study drug prior to the clinic visit on Day 7 as study drug will be administered on site.

5.1.4. Day 7 (±1), Treatment Periods 1 and 2

The following procedures will be performed, and assessments/measurements recorded:

- Review subject dosing diary
- Vital signs (BP, HR, respiration rate, and oral/tympanic temperature); for assessments of orthostatic changes, BP and HR are obtained: a) after rest in a supine position for at least 5 minutes, and b) 1 minute after standing:
 1. Within 30 minutes prior to dosing study drug
 2. Approximately 4 hours after dosing study drug
- 12-lead ECG, obtained 3 times (separated by approximately 1 minute) after subject has rested in supine position for at least 5 minutes:
 1. Within 30 minutes prior to dosing study drug
 2. Approximately 1 hour after dosing study drug
 3. Approximately 2 hours after dosing study drug
 4. Approximately 4 hours after dosing study drug
- C-SSRS
- Laboratory tests (hematology, chemistry, and urinalysis) at approximately 4 hours post-dose
- PK samples:
 1. Within 15 minutes prior to dosing study drug (CST-2032 and CST-107 or matching placebos)
 2. 30 minutes (+15 minutes) after administration of study drug
 3. 1 hour (+30 minutes) after dosing study drug
 4. 2 hours (+30 minutes) after dosing study drug
 5. 4 hours (+30 minutes) after dosing study drug
- Administer study drug (CST-2032 and CST-107 or matching placebos) from the Days 1-7 blister card/bottle
- Collect study drug (CST-2032 and CST-107 or matching placebos) blister cards/bottles from Days 1-7 and conduct accountability
- pVFT, DSST, CANTAB tests 3 hours (\pm 30 minutes) after dosing study drug. Tests should be conducted at approximately the same time of day (\pm 1 hour) and under the same food status on Days -1, 1, 7 and 14.
- Color Trails Test (select sites only), administered after CANTAB
- Assessment of AEs
- Assessment of concomitant medications
- Obtain blister card numbers/bottle for study drug (CST-2032 and CST-107 or matching placebos) from the IWRS and dispense study medication for Days 8-14
- Schedule Day 14 Visit. Subjects should be instructed not to administer study drug prior to the clinic visit on Day 14 as study drug will be administered on site.

5.1.5. Day 14 (± 1), Treatment Periods 1 and 2 / Early Withdrawal (EW*)

The following procedures will be performed, and assessments/measurements recorded at the Day 14 Visit of each Treatment Period. Subjects who withdraw prior to Day 14 should complete Day 14 safety assessments at the time of EW (identified with an asterisk [*]):

- *Review subject dosing diary
- *Vital signs (BP, HR, respiration rate, and oral/tympanic temperature); for assessments of orthostatic changes, BP and HR are obtained: a) after rest in a supine position for at least 5 minutes, and b) 1 minute after standing:
 1. Within 30 minutes prior to dosing study drug
 2. Approximately 4 hours after dosing study drug
- *12-lead ECG, obtained 3 times (separated by approximately 1 minute) after subject has rested in supine position for at least 5 minutes:
 1. Within 30 minutes prior to dosing study drug
 2. Approximately 1 hour after dosing study drug
 3. Approximately 2 hours after dosing study drug
 4. Approximately 4 hours after dosing study drug
- *C-SSRS
- Laboratory tests approximately 4 hours post-dose
 1. *Hematology, chemistry, and urinalysis
 2. *Serum or urine pregnancy test (per standard site practice) prior to dosing study drug for females of childbearing potential; positive urine pregnancy result to be confirmed by serum test
 3. Plasma sample for neurodegenerative biomarkers
- Administer study medication (CST-2032 and CST-107 or matching placebos) from the Days 8-14 blister cards or bottles
- *Collect study drug (CST-2032 and CST-107 or matching placebos) blister cards/bottle from Days 8-14 and conduct accountability
 - FERT administered at least 2 hours after dosing study drug and prior to administration of the cognition tests (pVRT, DSST, CANTAB)
 - pVFT, DSST, CANTAB tests 3 hours (\pm 30 minutes) after dosing study drug. Tests should be conducted at approximately the same time of day (\pm 1 hour) and under the same food status on Days -1, 1, 7 and 14.
 - Color Trails Test (select sites only), administered after CANTAB
 - SAS-6, CAARS, GDS-30 administered at least 2 hours after dosing study drug
 - MoCA
 - ADCS-CGIC
 - *Assessment of AEs
 - *Assessment of concomitant medications
 - *Register visit in IWRS

- Schedule End-of-Study Visit (TP2 Day 14 or EW Visit only)

5.1.6. End-of-Study – Approximately 7-12 Days after Treatment Period 2 Day 14 or EW Visit

The following procedures will be performed, and assessments/measurements recorded:

- Vital signs (BP, HR, respiration rate, and oral/tympanic temperature); for assessments of orthostatic changes, BP and HR are obtained: a) after rest in a supine position for at least 5 minutes, and b) 1 minute after standing
- 12-lead ECG, obtained 3 times (separated by approximately 1 minute) after the subject is supine for at least 5 minutes
- Symptom-driven physical examination
- Laboratory tests
 1. Hematology, fasting chemistry, and urinalysis
 2. Serum or urine pregnancy test (per standard site practice) for females of childbearing potential; positive urine pregnancy result to be confirmed by serum test
- C-SSRS
- Assessment of AEs
- Assessment of concomitant medications
- Register visit in IWRS

The End-of-Study Visit should be conducted in the clinic. However, should there be factors and/or conditions which would make the End-of-Study site visit unnecessarily difficult and/or potentially unsafe for a subject, this visit may be performed by alternate arrangement, e.g., visit in the subject's home, virtual visit.

5.2. Procedures for Monitoring Subject Compliance

All study procedures are to be performed under the direct supervision of the Investigator and qualified healthcare professionals at the study site unless conditions prevent the subject from safely attending. In these cases, study procedures may be performed by alternate arrangement, e.g., visit to the subject's home, virtual visit. The study site will maintain contact information for each subject; if a subject fails to return for study visits, the study site will make every attempt to contact the subject, including, but not limited to, sending registered letters.

5.3. Procedures and Specifications

5.3.1. Medical History, Vital Signs, and Physical Exam

Medical history, including details regarding illnesses and allergies, date(s) of onset, and whether condition(s) is currently ongoing, and medication history, will be collected on all subjects during Screening.

Subject height and body weight will be measured at Screening, and subject's BMI will be calculated and recorded.

Assessment of vital signs will include BP, HR, respiration rate, and oral/tympanic temperature. All routine measures of BP and HR should be collected (a) after rest in a supine position for at least 5 minutes, and (b) 1 minute after standing, to assess orthostatic changes. Vital signs will be collected as indicated in the [Schedule of Events](#).

A complete physical exam will be performed at Screening and will include general appearance and examination of the following body systems (excludes breast, genital, and rectal exams): head, neck and thyroid, eyes, ears, nose, throat, mouth, chest, respiratory, cardiovascular, lymph nodes, abdomen, skin, nails, hair, musculoskeletal, and neurological. A symptom-driven physical exam based on subject complaints will be conducted at the End-of-Study Visit.

5.3.2. 12-Lead ECG

A 12-lead ECG will be collected in triplicate as indicated in the [Schedule of Events](#). Subjects will be required to rest in a supine position for at least 5 minutes prior to the recording of ECG. All ECGs will be reviewed by the Investigator or qualified study staff and will be read by a central reader.

5.3.3. Clinical Laboratory Analysis

The following laboratory assessments will be performed at timepoints detailed in the [Schedule of Events](#):

Hematology: hematocrit, hemoglobin, mean corpuscular hemoglobin (MCH), mean corpuscular hemoglobin concentration (MCHC), mean corpuscular volume (MCV), platelet count, red blood cell (RBC) count, and white blood cell (WBC) count with differential, reticulocyte count.

Chemistry: albumin, alkaline phosphatase (ALP), alanine aminotransferase (ALT), aspartate aminotransferase (AST), BUN, calcium, bicarbonate, serum creatinine, creatine phosphokinase (CPK), glucose, lipase, amylase, phosphate, potassium, sodium, total bilirubin, total cholesterol, total protein, triglycerides, and uric acid.

Urinalysis: Appearance, occult blood, glucose, leukocyte esterase, nitrite, pH, protein, urobilinogen by dipstick; a reflex microscopic urinalysis will be performed if dipstick protein, nitrite, leukocyte esterase, or occult blood results are positive.

Calculated creatinine clearance according to the Cockcroft-Gault equation: To be determined at Screening only.

Serologies for HIV, hepatitis B, and hepatitis C: HbsAg, HbsAb, and HCV Ab (Screening only). If these results indicate potential infection, the PI must refer the subject for counselling and treatment as per institution policy and procedures.

SARS-CoV-2: Conducted at Screening by central lab. After Screening, the test may be conducted according to current local COVID management procedures.

Pregnancy Tests: Serum β -hCG for all female subjects of childbearing potential at Screening; serum or urine pregnancy test for women of childbearing potential on days noted in the [Schedule of Events](#). Positive urine pregnancy tests must be confirmed by a serum test.

Urine Drug Screen: Tests for drugs of abuse.

Alcohol breath test.

CST-2032 and CST-107 PK samples: Plasma samples will be collected for PK analysis on Day 7 of each treatment period for analysis of CST-2032, CST-107 and possible metabolites. Samples may be stored for up to 2 years.

Disease Biomarkers: Whole blood will be collected for analysis of genetic variants including but not limited to APOE4, LRRK2, and GBA (optional and where applicable) during screening, and plasma will be collected during screening and on Day 14 for analysis of neurodegeneration biomarkers (may be stored for up to 5 years).

Instructions on blood and plasma sample processing and shipping can be found in the Laboratory Manual.

Retesting Procedures:

Retesting of labs is only permitted if there is reason to believe that the retest value will be within acceptable parameters, such as if the initial test result was erroneous due to a sample processing error.

5.3.4. Pregnancy Testing

A serum β -hCG pregnancy test will be performed for all female subjects of childbearing potential at the Screening visit; female subjects may not be enrolled until the result of this test is known. FSH test will be performed for postmenopausal women. Women of childbearing potential will have serum or urine pregnancy tests on days noted in the Schedule of Events. Positive urine pregnancy tests will be confirmed by a serum test.

5.3.5. Columbia Suicide Severity Rating Scale (C-SSRS)

The C-SSRS, is a suicidal ideation and behavior rating scale to evaluate suicide risk (Posner 2011). It rates an individual's degree of suicidal ideation on a scale, ranging from "wish to be dead" to "active suicidal ideation with specific plan and intent and behaviors." The scale identifies specific behaviors which may be indicative of an individual's intent to complete suicide. The tool is administered by a qualified rater via interview with the subject.

5.3.6. Clinical/Disease and Cognitive Scales and Assessments

Clinical/disease and cognitive scales and assessments must be administered by an appropriately qualified rater. Clinical and cognitive scales will be conducted for all subjects unless otherwise stated and will be performed as outlined on the [Schedule of Events](#). The descriptions of these clinical/disease and cognitive scales are noted below.

5.3.6.1. Digital Symbol Substitution Test (DSST)

The DSST integrates complex neuropsychological processes and measures aspects of cognitive function, including cognitive and psychomotor speed, attention, visual scanning, and executive function. The specific version of the DSST used in this study is the Coding subtest of the Wechsler Adult Intelligence Scale – 4th edition (WAIS-IV).

Subjects are asked to copy simple graphic symbols that are paired to the digits 1–9 within a specified time period. Using a key, the examinee is asked to draw each symbol under its corresponding number. The examinee's score is determined by the number of symbols correctly drawn within a 90 or 120-second time limit. Higher scores indicate better performance; for a 120-second limit, the maximum attainable score is 135. Test scores can be benchmarked against published normative data by age group, and education level (2008 NCS Pearson, Inc.) as a means of evaluating test performance.

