8.4 Clinical and Cognitive Scales

The Montreal Cognitive Assessment (MoCA) is a brief cognitive screening tool and includes measures of expressive and receptive language, memory, and praxis. There are items that screen executive functions and working memory. The scores range from 0 to 30 with scores lower than 26 suggesting cognitive disorder.

The Digital Symbol Substitution Test (DSST) integrates complex neuropsychological processes and measures aspects of cognitive function, including cognitive and psychomotor speed, attention, visual scanning, and executive function. The maximum attainable score is 135, with higher scores indicating better performance. Further details of the test can be found in Section 5.3.6.1 of the study protocol.

The Modified Hoehn and Yahr Scale (MHYS, for PD subjects only) is a clinician-completed rating scale that is used to describe the symptom progression of PD. It parses PD into 5 stages, with the additional of stages 1.5 and 2.5 to account for the intermediate course of PD. Details on staging can be found in Section 5.3.6.8 of the study protocol.

The REM Sleep Behavior Disorder Single-Question Screen (RBD1Q) is a single “yes-no” question as follows: “Have you ever been told, or suspected yourself, that you seem to ‘act out your dreams’ while asleep (for example, punching, flailing your arms in the air, making running movements, etc.)?” RBD1Q will be evaluated for all subjects but used to assess eligibility for only PD subjects.

MoCA, DSST, MHYS, and RBD1Q data will be summarized in the demographics and baseline characteristics tables and listed by subject.

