9.3 Exploratory Endpoints and Analyses

The FAS will be used for all exploratory endpoint analyses unless stated otherwise.

Neurodegenerative Biomarkers

Neurodegenerative biomarkers including neurofilament light chain, total and phosphorylated tau protein, and amyloid- β (A β) peptides will also be collected at Screening and Day 14 of each treatment period. If data is available descriptive statistics of the neurodegenerative biomarkers and change from baseline to Day 14 will be summarized. Additionally, genetic biomarkers including APOE4, LRRK2, and GBA may be collected at Screening and descriptive statistics may be tabulated if numeric. All biomarker data will be listed.

Z-scores

Z-scores will be calculated for the observed values of select CANTAB, pVFT, and DSST endpoints using the formula: $z = (\text{observed value} - \text{normative mean}) / \text{normative SD}$. Normative means and standard deviations can be found in Appendix 3, and specifics on which parameters will be used in z-score derivations (ATT2BDM, PALTEA, RTIFMDRT, SSTSSRT, and VRMFR11D) are in section 9.2 in the CANTAB section. Z-scores will also be derived for the Alphabet and Category total scores of pVFT and the DSST total score. For the endpoints of PALTEA, RTIFMDRT and SSTSSRT, in which higher scores reflect poor performance, the sign of z-scores will be reversed by multiplying the calculated z-score by -1. Hence a positive z-score will reflect an outcome better than the norm and a negative z-score will reflect an outcome worse than the norm. In the case of the adaptive tracking test in the CANTAB, normative data are from prior studies conducted by CuraSen. For endpoints for which multiple norms are shown in Appendix 3, pooled estimates of the normal mean and SD, weighted by the sample size, will be used to calculate the z-scores. Z-scores for DSST will use norms based on the age of the subject. Normative data for the CANTAB, VFT, and DSST endpoints are summarized in Appendix 3. Normative data for the verbal fluency tests, DSST and most of the tests within the CANTAB are defined from published studies in which the tests were administered in an approximately similar manner as the CLIN-011 study. Normative data are based on untreated, approximately age matched cognitively normal populations, except for the Stop Signal Test where data are only available for a young adult population are available.

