Summary statistics of z-scores and change from baseline for subjects with a baseline deficit will be presented for each of the 5 CANTAB parameters marked. Baseline deficit is defined as having a baseline z-score less than -0.5. Subjects with baseline values greater than or equal to -0.5 will not be summarized. Additionally, a mixed model approach will be used to evaluate treatment effect. The model will include change from baseline in z-score as the dependent variable, baseline as a covariate, treatment sequence, period, timepoint (i.e., Day 1: 3 hrs post-

hose, Day 7: 3 hrs post-dose, Day 14: 3 hrs post-dose), disease type, and treatment as fixed effects, and subject as a random effect. The least square means will be summarized, as well as the least square mean difference between treatments, where the corresponding p-value for this LS mean difference will be provided.

Summary statistics of z-scores and change from baseline for subjects with a baseline deficit for the two pVFT parameters will also be presented. Baseline deficit is defined as having a baseline z-score less than -0.5, and subjects with baseline values greater than or equal to -0.5 will not be summarized. Additionally, a mixed model with z-score change from baseline as the dependent variable, baseline as a covariate, treatment sequence, period, timepoint (i.e., Day 1, Day 7, Day 14), disease type, and treatment as fixed effects, and subject as a random effect will be analyzed, with the least square means, least square mean difference, and corresponding p-value will be provided.

Summary statistics of z-scores and change from baseline for subjects with a baseline deficit for DSST total score will be presented. Baseline deficit is defined as having a baseline z-score less than -0.5, and subjects with baseline values greater than or equal to -0.5 will not be summarized. Additionally, a mixed model with z-score change from baseline as the dependent variable, baseline as a covariate, treatment sequence, period, timepoint (i.e., Day 1, Day 7, Day 14), disease type, and treatment as fixed effects, and subject as a random effect will be analyzed, with the least square means, least square mean difference, and corresponding p-value will be provided.

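### Protocol 5.3.6.1 permits a 90- or a 120-second DSST, but the SAP's maximum score and its only DSST norms fit 120 seconds alone

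*Protocol*

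**What the plan says.** Protocol 5.3.6.1 names one instrument: "The specific version of the DSST used in this study is the Coding subtest of the Wechsler Adult Intelligence Scale", fourth edition. It then states that the "score is determined by the number of symbols correctly drawn within a 90 or 120-second time limit". It does not choose between the two limits. It adds that "for a 120-second limit, the maximum attainable score is 135" and gives no maximum for 90 seconds.

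SAP 8.4 drops the condition: "The maximum attainable score is 135, with higher scores indicating better performance". For further detail it sends the reader back to Protocol 5.3.6.1.

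SAP 9.3 converts the DSST total to a z-score by subtracting a normative mean and dividing by a normative SD. "Z-scores for DSST will use norms based on the age of the subject"; the time limit plays no part. Appendix 3 prints one set of DSST norms, labelled as two-minute norms. Only a subject whose z-score at baseline lies below -0.5 counts as deficient, and all others are left out of this analysis. For those who qualify, the plan is: "Summary statistics of z-scores and change from baseline for subjects with a baseline deficit for DSST total score will be presented".

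The DSST is a secondary endpoint (Protocol 2.3). SAP 9.2 analyses its change from baseline in a mixed model that has no term for the time limit.

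**The concern.** A DSST score is a count of symbols completed in a fixed time, so scores from 90 and 120 seconds are on different scales. The protocol text allows both, while the SAP can score only one correctly. Neither document gives 90-second norms, a conversion, or a rule to record the limit used. The schedule of events standardises time of day and food status for the test but is silent on its duration, and up to 20 sites are planned.

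Two analyses are exposed. In the exploratory z-score analysis, a 90-second count set against two-minute norms looks worse than it is and can push a subject below the deficit cut. In the secondary raw-score analysis, a change of limit between a subject's baseline and later visits would appear as a change in performance.

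**Working it through.** The documents state no figure for this point, so there is none to reproduce. I applied the SAP's own rule to its own norms.

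**Inputs.** DSST means and SDs from SAP Appendix 3, for the bands that overlap the enrolled age range of 50 to 85 years (Protocol 4.2); the deficit cut of z < -0.5 from SAP 9.3. One input is an assumption: r, the 90-second score as a share of the 120-second score. A constant copying pace gives r = 90/120 = 0.75. I show 0.75 to 0.90.

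**Formulas.** A subject exactly at the age norm scores the normative mean at 120 seconds, so z = 0 and there is no deficit. Stopped at 90 seconds, the same subject scores r × mean, so

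- z = (r × mean - mean)/SD = -(1 - r) × mean/SD
- raw score at the cut = mean - 0.5 × SD
- break-even r, where z = -0.5, is 1 - 0.5 × SD/mean

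Example, 70-74 years at r = 0.75: 0.75 × 49.5 = 37.1; z = (37.1 - 49.5)/15.5 = -0.80; the cut is 49.5 - 7.75 = 41.75.

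| Age band (years) | Mean / SD | Raw score at cut | 90-s score, r = 0.75 | z, r = 0.75 | z, r = 0.80 | z, r = 0.85 | z, r = 0.90 | Break-even r |
|---|---|---|---|---|---|---|---|---|
| 45-54 | 65.0 / 16.0 | 57.0 | 48.8 | -1.02 | -0.81 | -0.61 | -0.41 | 0.877 |
| 55-64 | 59.5 / 15.5 | 51.75 | 44.6 | -0.96 | -0.77 | -0.58 | -0.38 | 0.870 |
| 65-69 | 54.4 / 15.5 | 46.65 | 40.8 | -0.88 | -0.70 | -0.53 | -0.35 | 0.858 |
| 70-74 | 49.5 / 15.5 | 41.75 | 37.1 | -0.80 | -0.64 | -0.48 | -0.32 | 0.843 |
| 75-79 | 44.5 / 16.0 | 36.5 | 33.4 | -0.70 | -0.56 | -0.42 | -0.28 | 0.820 |

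The average performer is classed as deficient in all five bands for r up to about 0.82, in the three bands from 45 to 69 years at 0.85, and in none above about 0.88.

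**Share of a normal reference group below the cut.** At 120 seconds it is Φ(-0.5) = 31%. At 90 seconds with r = 0.75, and the SD shrinking in proportion, it is Φ((-0.5 + 0.25 × mean/SD)/0.75), which runs from 60% (75-79 years) to 75% (45-54 years). If the SD does not shrink, the range is 58% to 70%.

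**Raw score.** A switch of limit between baseline and a later visit moves a subject at the norm by (1 - r) × mean. At r = 0.75 this is 0.25 × 44.5 = 11.1 to 0.25 × 65.0 = 16.3 points. At r = 0.90 it is 4.5 to 6.5 points.

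**The case against.** The strongest reply is that the study limit is 120 seconds and the 90-second wording is loose description. The protocol names a single version for the whole study. Its only stated maximum belongs to 120 seconds, and the SAP repeats that maximum without condition. The Appendix 3 norms are two-minute norms. Where sites may differ, as with the Color Trails Test, the documents say so, and the DSST must be given by a qualified rater. Most of this stands: 120 seconds is very probably what was intended. It does not remove the conflict, because the section that names the version is the one that gives two limits, and the SAP refers back to it.

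A reader might infer more than the documents support:

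- *That some sites or visits used 90 seconds.* Nothing shows this, and rater instructions and the case report form are not available here.
- *That an average 90-second performer is always classed as deficient.* This depends on r, which the documents do not give.
- *That every subject is scored against the two-minute norms.* The norms as printed stop at 79 years, while enrolment runs to 85.
- *That the treatment comparison on raw scores is biased.* If each subject keeps one limit, the within-subject contrast is only rescaled. A false shift needs a change of limit within a subject.

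Enrolled subjects also have diagnosed impairment and a MoCA of 14 to 26, so many would fall below -0.5 at 120 seconds anyway. The calculation for a subject at the norm shows the size of the bias, not the expected number misclassified.

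**Conclusion.** The protocol permits a DSST time limit that the SAP cannot score correctly. This is a real conflict between stated rules, but a conditional one and of minor severity. Any 90-second score would have its z-score lowered by (1 - r) × mean/SD for a subject at the norm: 0.70 to 1.02 at constant pace, and 0.28 to 0.41 at r = 0.90. The first range carries an average performer past the deficit cut in every printed band; the second does so in none.

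The conclusion rests on two things the documents do not settle: whether 90 seconds was used anywhere, and the value of r. The z-score analysis is exploratory, as SAP section 9 says of all inferential analyses. Eligibility and the primary safety endpoint are not affected.

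**What to change.** 1. In Protocol 5.3.6.1, delete the 90-second alternative, so that every DSST administration uses the 120-second limit that matches the SAP maximum and norms.
2. Before database lock, confirm with each site and record the limit used at each DSST visit. If all used 120 seconds, one sentence saying so closes the point.
3. In SAP 9.3, derive DSST z-scores and deficit status only from 120-second scores.
4. In SAP 9.2, exclude from the raw change analysis only subjects whose limit differed between visits, or show them in a sensitivity analysis. Subjects tested at 90 seconds throughout can stay, since their changes are internally consistent.

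The cost is one phrase in the protocol, two sentences in the SAP, a small check of the limit used, and possibly a few excluded scores. Any site now using 90 seconds would need 30 more seconds per test. Step 3 works only if step 2 is done, because the exclusion needs a known limit.
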